9.1.2.1 Treatment Period

During Visit 2, the following assessments will be completed before the subject receives their first dose of study drug: MMSE, CDR, ADAS-cog14, FAQ, and NPI-10. These assessments will provide baseline measurements for the study. For any given subject, every effort should be made to ensure that the CDR rater remains unchanged throughout the study. (revised per Amendment 03) Inclusion and exclusion criteria will be reviewed again together with concomitant medications and assessment of AEs. A single 12-lead ECG will be conducted. All ECG recordings will be evaluated by a central reader. The C-SSRS will also be administered. A baseline routine physical examination with dermatologic review, vital signs measurements, clinical laboratory testing (including viral characterization), urinalysis using urine dipstick, and a urine pregnancy test (females of child-bearing potential only), will be performed. Additional blood samples will be taken for PD/exploratory biomarkers and immunologic assessments. (revised per Amendment 03) Some of the immunologic assessment blood sample will be used to prepare isolated PBMCs which will be stored for testing as needed. (revised per Amendment 02) The results of some of the immunologic assessments will be provided to the DSMB for periodic review during the Core Study. (revised per Amendment 05) Whilst there is no prescribed order in which the assessments at each visit are to be performed, the subject component of the cognitive, functional and quality of life assessments are to be performed in the morning whenever possible, or consistently at the same time of the day and ideally should be completed before the more invasive procedures (eg, physical examination, ECG, blood draw).

Subjects will be randomized at Visit 2 (Day 1) to receive elenbecestat 50 mg per day or placebo administered orally QD in the morning with or without food. Subjects will be encouraged to stay at the site for observation for at least 30 minutes following their first dose of study drug. The duration of this observation period can be extended at the investigator's discretion, eg, if warranted by medical history or concomitant medication (revised per Amendment 03). Double-blinding to study drug will be in effect throughout the Treatment Period.

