Blood samples will be collected for PD/exploratory biomarker assessments as specified in Table 4 and Table 5. (revised per Amendment 02) The blood sample collected for PD analyses at Visit 2 should be collected at fasting or at least 2 hours after the most recent meal and PD blood samples should be taken predose at Visits 3, 4, 6, 7, 9, 11, and 13 (or ED) and, as far as is feasible, samples should be taken at the same time of day. (revised per Amendment 03)

Prerandomization blood samples for immunologic assessments and CSF (if applicable) will also be stored for determination of prior exposure to any suspected infective agents in the

event that the subject develops TEAEs that warrant further investigation (eg, treatment-emergent infection). (revised per Amendments 02 and 03) Testing may include, but not be limited to, serological tests (eg, HSV1 and 2), viral titer by quantitative polymerase chain reaction (Q-PCR), and/or human leukocyte antigen (HLA) genotyping.

For all subjects, baseline and on-study blood samples, DNA samples, and any collected CSF samples (if applicable) will be stored for up to 15 years.

See the laboratory manual (to be supplied to study sites) for a description of the collection, handling, and shipping procedures of the biomarker samples.

Pharmacogenomics

A blood sample will be obtained at Screening and will be used to determine the *ApoE* genotype of all subjects enrolled in this study. NAT2 genotype will be evaluated in a subset of subjects. Genotype will be determined from blood specimens using validated assays. (revised per Amendment 03) The findings will be used in the statistical analysis to determine the effects on treatment response and safety.

The genomic DNA samples will be stored and may also be used to examine the role of genetic variability in subjects' absorption, distribution, metabolism, and excretion, the development of AEs, or underlying AD. Variations in elenbecestat exposure or the occurrence of AEs observed in the study population may be evaluated by correlation of single-nucleotide polymorphisms with PK, safety, or PD data.

Details of PGx testing may be provided and reported separately.

Amyloid PET

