9.7.1.6.1 PRIMARY EFFICACY ANALYSIS

The primary analysis will be based on an intent to treat philosophy without regard to adherence to treatment. The primary analysis of the change from baseline in CDR-SB at 24 months will be performed to compare elenbecestat 50 mg per day versus placebo using a linear mixed effects model for repeated measures (MMRM) on the FAS. The MMRM model will include fixed effects of treatment group, visit, treatment group by visit interaction, baseline CDR-SB, baseline CDR-SB by visit interaction, and randomization stratification variables (ie, region [7 levels], clinical dementia [yes, no], and concurrent AD medication use at randomization [Visit 2] [yes, no]). *ApoE4* status may be included in the model if appropriate. (revised per Amendment 05) An unstructured covariance matrix will be employed to model the covariance of within subject effect; if MMRM fails to converge then a covariance structure with fewer parameters from the following list will be employed according to the prespecified order in the list until the MMRM converges. The list of covariance structure will include Heterogeneous Toeplitz, Toeplitz, Heterogeneous Compound Symmetry, and Compound Symmetry. This primary analysis will include all observed post baseline data of the change from baseline in CDR-SB without imputation of missing values. The treatment effect for elenbecestat versus placebo will be compared at

24 months based on MMRM model. The LS means and difference in LS means between elenbecestat treatment group and placebo, and corresponding 95% CI will be presented.

The null hypothesis is that there is no difference in the mean change from baseline in CDR-SB at 24 months between elenbecestat 50 mg per day and placebo. The corresponding alternative hypothesis is that there is a difference in the mean change from baseline in CDR-SB at 24 months between elenbecestat 50 mg per day and placebo.

The primary analysis will be repeated to minimize the impact of change in concomitant AD medications where efficacy data after initiation of new AD medications and increase of current AD medications will be censored.

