9.7.2 Determination of Sample Size

The sample size for this study is estimated for comparison of elenbecestat versus placebo with respect to a pooled analysis of studies E2609-G000-301 and E2609-G000-302 for the change from baseline in CDR-SB at 24 months. Based on the available data from the placebo group in Study BAN2401-G000-201 (a recently completed study with a comparable subject population), the mean and the standard deviation of the change from baseline in CDR-SB at 24 months in the placebo group are assumed to be 1.46 and 2.05, respectively, instead of 1.75 and 2.05, which are originally assumed by the available data from ADNI (of amyloid positive, MMSE equal or greater than 24, late MCI [global CDR=0.5, CDR memory box \geq 0.5]). Therefore, assuming a 25% reduction in the mean change from baseline CDR-SB at 24 months for elenbecestat compared to placebo with common standard deviation of 2.05 and 30% dropout rate, a total sample size of 1900 subjects, 950 subjects in each treatment group, will be required to detect the treatment difference between elenbecestat and placebo using a 2-sample t test with 90% power at a significance level of 2 sided alpha =0.05.

The pooled data from 2 studies (E2609-G000-301 and E2609-G000-302) will comprise the total sample size of approximately 1900 subjects. At least 850 subjects will be randomized in each study. (revised per Amendment 05)

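### The primary MMRM omits baseline ADAS-cog14 and FAQ and leaves ApoE4 optional: a modest missed gain in precision, not an error or a power shortfall

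*Protocol*

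**What the plan says.** Protocol 9.7.1.6.1 specifies the primary MMRM with treatment, visit, their interaction, baseline CDR-SB, baseline CDR-SB by visit, and the stratification factors: region (7 levels), clinical dementia (yes/no) and concurrent AD medication (yes/no). The fallback covariance structures are listed in a fixed order. One covariate is left open: ApoE4 "status may be included in the model if appropriate". No criterion or decision time is given.

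The same clause recurs for the multiple-imputation ANCOVA in that section and, in 9.7.1.6.2, for the slope model, both Cox models and the ANCOVA relating clinical to biomarker change. The ADCOMS and amyloid PET analyses reuse the primary model, so they inherit the open term.

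The extra baseline data are already planned:

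- Section 9.1.2.1 has MMSE, CDR, ADAS-cog14, FAQ and NPI-10 completed at Visit 2 before the first dose. "These assessments will provide baseline measurements for the study".
- Section 9.5.1.4.2 uses a Screening blood sample to determine the ApoE "genotype of all subjects enrolled in this study", and Table 2 marks ApoE as mandatory.
- Appendix 4 makes an exception where national law prohibits collecting or using such samples.

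The sample size (9.7.2) was set "using a 2-sample t test with 90% power at a significance level of 2 sided alpha =0.05". It takes no credit for any covariate.

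**The concern.** Adjusting a randomized comparison for baseline variables that predict the outcome narrows the standard error of the treatment contrast. The plan collects several candidates and uses only the endpoint's own baseline plus the stratification factors.

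There is reason in the protocol to expect some further information. Section 9.2.3 describes the FAQ as likely to track AD progression and the 14-item ADAS-cog as more sensitive in less impaired subjects. Entry requires a global CDR of 0.5, which restricts the range of baseline CDR-SB. Neither ADAS-cog14 nor FAQ is an entry criterion.

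What is at stake is mainly precision that could be had without new data. A lesser matter is that the confirmatory model has two admissible forms, with and without ApoE4, and the protocol does not say when the choice will be made.

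**Working it through.** **Inputs (Protocol 9.7.2).** Mean and SD of change "in the placebo group are assumed to be 1.46 and 2.05, respectively"; effect "assuming a 25% reduction in the mean change from baseline CDR-SB at 24 months"; "common standard deviation of 2.05 and 30% dropout rate"; "a total sample size of 1900 subjects, 950 subjects in each treatment group".

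**Reproducing the plan's figure.**

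- Difference: 0.25 × 1.46 = 0.365.
- Evaluable per arm: 2 × (1.960 + 1.282)² × 2.05² / 0.365² ≈ 663.
- With 30% dropout: 663 / 0.70, rounded up, = 948 per arm, or 1896 in total against 1900 stated.
- Power with 950 × 0.70 = 665 evaluable per arm: SE = 2.05 × √(2/665) = 0.1124; 0.365 / 0.1124 = 3.247; Φ(3.247 − 1.960) = 0.901. The noncentral t gives 0.900.

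The stated sample size therefore holds with no covariate adjustment.

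**Effect of adding covariates.** Let R² be the share of the variance 2.05² explained by the added terms. The protocol gives no value, so the range is an assumption. The residual SD is 2.05 × √(1 − R²), with 665 evaluable per arm.

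| Assumed R² | Residual SD | Power | N for 90% power | Saving against 1896 | 95% CI half-width |
|---|---|---|---|---|---|
| 0% | 2.050 | 90.1% | 1896 | 0 | 0.220 |
| 1% | 2.040 | 90.4% | 1878 | 18 | 0.219 |
| 2% | 2.029 | 90.7% | 1858 | 38 | 0.218 |
| 5% | 1.998 | 91.5% | 1802 | 94 | 0.215 |
| 10% | 1.945 | 92.8% | 1706 | 190 | 0.209 |

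**Why these are upper figures.** The table starts from the raw SD, but the planned MMRM already adjusts for baseline CDR-SB and clinical dementia. As an illustration, suppose the current terms explain 10% (also assumed):

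- Power already stands at 92.8%.
- If the new terms remove 5% of what remains, the residual share is 0.90 × 0.95 = 0.855.
- SE = 2.05 × √0.855 × √(2/665) = 0.1040, and power = Φ(0.365/0.1040 − 1.960) ≈ 94.0%.
- The gain is about 1.1 points, compared with 91.5 − 90.1 = 1.4 points when counted from the raw SD.

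**The open ApoE4 term, worst case only.** If both fits were run unblinded and the smaller p-value reported, the type I error would be P(max(|Z₁|, |Z₂|) > 1.96), with correlation about √(1 − R²) between the two statistics. For an ApoE4 R² of 1%, 5% or 10% this is 5.5%, 6.0% or 6.5%.

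**The case against.** The strongest reply is that the model is complete and valid as it stands. It adjusts for the endpoint's own baseline and every stratification factor, one of which, clinical dementia, is itself a severity measure. The sample size relies on no adjustment and is met. Which further covariates to add is a matter of judgement. Entry limits of global CDR 0.5 and MMSE of at least 24 also narrow the range over which other severity scores can predict. All of this stands. It limits the point to an efficiency gain of uncertain size.

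Adding ApoE4 also has a cost. Given the country-law exception in Appendix 4, genotype may be absent for whole countries. Without a missing-value rule, a forced ApoE4 term would drop those subjects from the analysis. A reader might infer from Table 2 that every subject will have a genotype; the protocol does not guarantee that.

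A reader might also infer that type I error is inflated. The documents do not support this. No section licenses fitting both models and choosing the better result, and an SAP finalised before unblinding would settle the matter; that SAP is not among the documents reviewed here. The 10% end of the range is also generous, since it gives ApoE4 alone all the variance that the table allows for three covariates together. What remains is narrower: 9.7.1.2 explicitly commits to settling the per-protocol criteria before database lock and unblinding, and the ApoE4 clause carries no such commitment.

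**Conclusion.** The point holds as a missed efficiency. Baseline ADAS-cog14 and FAQ are scheduled before dosing and ApoE genotyping is mandatory apart from the legal exception, yet the two scores are unused and ApoE4 is optional. On an assumed R² of 2% to 10% relative to SD 2.05, power would move from 90% to about 90.7% to 92.8%. The real gain would be lower to the extent that the current covariates already explain variance, and close to nothing if the extra R² is near zero.

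A reader might take the omission to mean that the study is underpowered or the analysis wrong. Neither follows, because 90% power is reached unadjusted. The open ApoE4 term is a secondary matter of clarity, and the 5.5% to 6.5% error rate is a worst case that the protocol does not provide for.

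**What to change.** Before any unblinded look at the data, including the futility analysis in 9.7.3:

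- Name baseline ADAS-cog14 and baseline FAQ, each with a by-visit term, and ApoE4 carrier status as fixed covariates in the primary MMRM.
- Add a missing-value rule so that no Full Analysis Set subject is lost, for example a missing-genotype category and simple imputation of a missing baseline score.
- Replace the optional ApoE4 clause with that decision wherever it appears in 9.7.1.6.1, 9.7.1.6.2 and the synopsis, and say whether the added terms carry over to the key secondary models.
- Report the primary model without ApoE4 as a sensitivity analysis.

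The cost is wording in the protocol and SAP and a short missing-data rule. No new assessments, samples or subjects are needed, and the sample size need not change.

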9.7.1.6.2 SECONDARY EFFICACY ANALYSES

Analyses for Key Secondary Efficacy Endpoints (revised per Amendment 05):

The key secondary analyses will be performed only if the primary analysis is significant. The treatment effect for elenbecestat 50 mg/day versus placebo, for each key secondary efficacy endpoint, will be tested using a sequential testing procedure at a significance level of 2-sided $\alpha = 0.05$, ie, any test will start only if the test with higher hierarchical order is significant.

The change from baseline in ADCOMS at 24 months will be analyzed using the same MMRM model as the primary efficacy analysis to compare elenbecestat 50 mg per day versus placebo on the FAS, using baseline ADCOMS in the model.

The change from baseline in amyloid PET SUVR at 24 months will be analyzed using the same MMRM model as the primary efficacy analysis to compare elenbecestat 50 mg per day versus placebo on the FAS, using baseline amyloid PET SUVR in the model. The same analysis will be performed within study as key secondary efficacy endpoint analyses.

Analyses for Other Secondary Endpoints (revised per Amendment 05)

The change from baseline in CDR-SB and ADCOMS at 24 months will be analyzed using the same MMRM model as the primary analysis for subjects enriched by baseline PET SUVR between e.g. 1.2 and 1.6 on the FAS.

The rate of change over time (mean slope) based on change from baseline in the CDR-SB will be analyzed using linear mixed effects (LME) models for multivariate normal data derived from a random coefficient model (slope analysis), where the mean slope in each group depends on a continuous assessment time. The LME model will include treatment group, baseline CDR-SB, randomization stratification variables, assessment time, baseline CDR-SB-by-assessment time, and treatment group-by-assessment time. ApoE4 status may be included in the model if appropriate.

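### The MMRM fallback order for the primary test is badly fixed: homogeneous Toeplitz precedes Heterogeneous Compound Symmetry, so the month-24 standard error could be too small if that step were reached (minor)

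*Protocol*

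**What the plan says.** Protocol section 9.7.1.6.1 compares the arms at 24 months with an MMRM on all observed post-baseline changes in CDR-SB. The covariance is unstructured. Only if that fit does not converge is a simpler structure taken from a list: "The list of covariance structure will include Heterogeneous Toeplitz, Toeplitz, Heterogeneous Compound Symmetry, and Compound Symmetry". The choice is mechanical, because each structure "will be employed according to the prespecified order in the list until the MMRM converges". The same text stands in the Synopsis under the primary efficacy analyses.

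Section 9.7.1.6.1 promises LS means and a 95% CI. It does not say whether standard errors are model-based or empirical.

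Section 9.7.1.6.2 analyses ADCOMS and amyloid PET SUVR "using the same MMRM model as the primary efficacy analysis", and the other continuous secondary endpoints likewise.

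The only SD given for CDR-SB change is the month-24 value in section 9.7.2, where the placebo mean and SD "are assumed to be 1.46 and 2.05, respectively".

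**The concern.** Toeplitz and Compound Symmetry, without the heterogeneous prefix, give every visit the same variance. The primary test concerns month 24 alone. If the SD of change grows over follow-up, the common variance falls below the month-24 variance, and a model-based standard error for the month-24 difference is too small.

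Growth is plausible here. Entry requires a CDR global score of 0.5 (section 9.3.1), so subjects start from a narrow range. The outcome is change from baseline in a progressive disease. The protocol's own slope analysis of CDR-SB (section 9.7.1.6.2) uses a random coefficient model, under which variance generally changes with time.

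The order makes this worse. Toeplitz is tried before Heterogeneous Compound Symmetry. If both would converge, the rule must take the homogeneous one and never reaches the other. At stake are the primary p-value and confidence interval, in the one situation for which the fallback exists.

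**Working it through.** **1. The plan's own figure.** Inputs from section 9.7.2: placebo mean 1.46, SD 2.05, 25% reduction, 30% dropout, two-sided alpha 0.05, 90% power.
- Difference = 0.25 × 1.46 = 0.365.
- Evaluable per arm = 2 × (1.960 + 1.2816)² × 2.05² / 0.365² = 663.
- Dropout: 663 / 0.70, rounded up, = 948 per arm, 1896 in total.

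The protocol states "a total sample size of 1900 subjects, 950 subjects in each treatment group", so the figure reproduces. It does not depend on the fallback order.

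**2. Size of each structure.** CDR is done every 3 months (section 9.1.2.1), which gives 8 on-treatment visits. Covariance parameters:
- Unstructured: 8 × 9 / 2 = 36
- Heterogeneous Toeplitz: 8 + 7 = 15
- Toeplitz: 1 + 7 = 8
- Heterogeneous Compound Symmetry: 8 + 1 = 9
- Compound Symmetry: 2

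Moving Toeplitz ahead of Heterogeneous Compound Symmetry saves one parameter the wrong way round: the listed order goes from 8 up to 9.

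**3. Closed form, complete data.** With complete data the month-24 contrast is the difference in month-24 means. Its model-based variance under Compound Symmetry uses the average of the visit variances. Hence

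SE ratio = √(mean of SDₜ² over 8 visits / 2.05²), and type I error = 2Φ(−1.96 × ratio).

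The month-3 SD is an assumption, and the SD is taken as linear in time up to 2.05. Only the ratios between visits matter.
- Month-3 SD 1.75: mean variance 3.620, ratio √(3.620 / 4.2025) = 0.928, type I error 0.069.
- 1.5: mean variance 3.183, ratio 0.870, type I error 0.088.
- 1.0: mean variance 2.444, ratio 0.763, type I error 0.135.

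If variance is instead proportional to time, the ratio is √(4.5 / 8) = 0.75 and the type I error is 0.142.

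**4. With dropout and correlation.** The large-sample model-based variance was compared with the true variance for three correlation shapes (autoregressive, exchangeable, a mixture) and for dropout of 0% or 30%, completely at random. Ranges cover these settings.

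| Assumed month-3 SD | Toeplitz: SE ratio | Toeplitz: type I error | CS: SE ratio | CS: type I error |
|---|---|---|---|---|
| 2.05 (no growth) | 1.00 | 0.050 | 0.95–1.00 | 0.050–0.063 |
| 1.75 | 0.921–0.929 | 0.069–0.071 | 0.879–0.928 | 0.069–0.085 |
| 1.5 | 0.857–0.873 | 0.087–0.093 | 0.821–0.870 | 0.088–0.108 |
| 1.25 | 0.797–0.822 | 0.107–0.118 | 0.764–0.815 | 0.110–0.135 |
| 1.0 | 0.741–0.776 | 0.128–0.146 | 0.709–0.763 | 0.135–0.165 |

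Heterogeneous Toeplitz gives 0.050 in every setting and Heterogeneous Compound Symmetry 0.039–0.050. If the SD fell from 2.4 to 2.05, Toeplitz would give 0.032 and Compound Symmetry 0.040. The direction therefore depends on growth.

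**5. Unconditional size.** Overall type I error = 0.05 + P(step reached) × (conditional error − 0.05). P is not known. With the highest Toeplitz figure above, 0.146, an assumed P of 1% gives 0.05 + 0.01 × 0.096 = 0.051, and an assumed P of 5% gives 0.05 + 0.05 × 0.096 = 0.055.

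**The case against.** A reader might infer from the list that the primary analysis as planned has an inflated type I error. The documents do not support that reading, for three reasons.
- **The step is remote.** Toeplitz is used only if the unstructured and Heterogeneous Toeplitz fits both fail, and Compound Symmetry only after four failures. With 36 parameters and about 1900 pooled subjects, failure of the first fit looks unlikely. That is a judgement, not a calculation. The first fallback holds the level.
- **The standard error is not specified.** Model-based errors are an assumption, and the SAP, which I have not seen, may name the estimator. With an empirical standard error the large-sample rate is 0.05.
- **Variance growth is assumed.** No SD by visit is given, and with a flat SD the Toeplitz rate is 0.050.

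All three stand, and they make the point conditional and minor.

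It is also tempting to say that every endpoint using this model shares the problem equally. It does not. Amyloid PET is scheduled only at 12 and 24 months. With two visits the unstructured matrix has 3 parameters and Heterogeneous Toeplitz is the same model. ADCOMS depends on six-monthly scales, so it has four on-treatment visits and 10 parameters.

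Finally, section 9.7.1.6.1 plans an ANCOVA after multiple imputation. It does not impose a common variance across visits and would expose a marked discrepancy in the standard error. It does not replace the primary test.

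None of this defends the order itself. The protocol writes the list and makes the sequence binding, so this is a stated rule and not a detail left open.

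**Conclusion.** The fallback order is badly fixed, and the consequence is conditional. Three things must hold together: a homogeneous structure is reached, standard errors are model-based, and the SD of CDR-SB change rises to 2.05 at month 24. For an assumed month-3 SD between 1.75 and 1.0, the month-24 standard error is then understated by about 7% to 26% under Toeplitz and 7% to 29% under Compound Symmetry. Conditional type I error is about 7% to 15% and 7% to 17% respectively.

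The unconditional excess is that amount multiplied by a probability that the documents do not give and that is probably small. Severity is minor. The point matters mainly for CDR-SB with its 8 visits, and hardly for amyloid PET.

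**What to change.** In section 9.7.1.6.1 and the matching Synopsis text, delete Toeplitz and Compound Symmetry from the list, or at least place both after Heterogeneous Compound Symmetry. Add that an empirical (sandwich) standard error is used whenever the fitted structure is not unstructured.

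The sandwich estimator corrects the standard error. It does not remove bias in the estimate if the covariance is misspecified and dropout depends on observed outcomes, so the heterogeneous structures should still come first.

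The cost is one sentence and slightly wider intervals if a fallback is ever used. The sample size is unaffected. The change should be made before unblinding, because a later one would look data-driven.
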